6. EFFICACY ANALYSES

All efficacy analyses will be based on Ontamalimab Responder FAS unless stated otherwise. Baseline for all efficacy analyses is defined as the last observed value for the efficacy assessment prior to taking the first dose of IP (based on dates or date/times) in the induction study (SHP647-301 or SHP647-302) unless otherwise specified. Maintenance baseline for all efficacy analyses is defined as the value for the efficacy assessment collected at the Week 12 visit of the induction study.

The collected data shown in Appendix 16.1 but removed from Appendix 16.2 will be listed for the FAS including Inflammatory Bowel Disease Questionnaire questions, Short Form-36 Health Survey form, hospitalizations, [REDACTED]

All efficacy analyses will be conducted according to the randomized treatment, regardless of the treatment actually received.

All confidence intervals (CIs) will be 2-sided 95% CIs, unless stated otherwise.

For continuous endpoints, descriptive summary statistics will be presented by treatment group at each scheduled visit and will include the following: n, mean, median, standard deviation, minimum, and maximum. For binary endpoints, number and percentage of subjects in each category will be summarized by treatment group at each scheduled visit.

Due to the early discontinuation of the study before full enrollment and the limited sample size, planned efficacy analyses have been updated.

6.1 Analyses of Primary Efficacy Endpoint

The primary efficacy endpoint is remission at the Week 52 visit. Remission is defined as a composite score of patient-reported symptoms using daily e-diary and centrally read endoscopy as follows:

- Stool frequency subscore of 0 or 1 with at least a 1-point change from induction (SHP647-301 or SHP647-302) baseline

AND

- Rectal bleeding subscore of 0

AND

- Endoscopic subscore of 0 or 1 (modified, excludes friability), based on centrally read results.

The primary efficacy endpoint will be compared for each active treatment group (25 mg or 75 mg ontamalimab) to the corresponding placebo group (25 mg in induction placebo group or 75 mg in induction placebo group; placebo groups are not pooled) using a Cochran-Mantel Haenszel (CMH) chi-square test stratified by actual status of glucocorticoid use at MNT (SHP647-303) baseline, prior anti-TNF treatment, and the degree of clinical response in the induction studies (whether remission is achieved or not). Subjects with the intercurrent events defined in Section 2.2 and/or with missing remission data at Week 52 will be considered failures and counted as nonresponders. Subjects with treatment failure will also be counted as nonresponders. Subjects with missing induction baseline value in SF subscore will be counted as remission if both SF and RB subscores are 0 and endoscopic subscore are either 0 or 1 at Week 52. The endoscopy score will be based on centrally read results.

The primary endpoint will be tested by the following hypothesis:

$$H_0: \delta = 0$$

$$H_1: \delta \neq 0$$

where δ is the common treatment difference across strata, $j=1$ to m . The common treatment difference is a weighted average of the stratum-specific treatment differences.

The estimate of the common treatment difference along with the corresponding stratified Newcombe 95% CI using the method of Yan and Su (2010) and CMH p-value will be presented for each active treatment group to the corresponding placebo group comparison.

6.1.1 Sensitivity Analyses of Primary Efficacy Endpoint

A sensitivity analysis will be performed using the CMH testing described in Section 6.1, including only the subset of subjects who had the opportunity to complete 52 weeks of treatment in the SHP647-303 study prior to the implementation of Protocol Amendment 3 at their site.

The primary efficacy endpoint will be summarized separately for the placebo responder FAS by treatment group without inferential methods. The number and percentage of subjects, and the estimate of the common treatment difference along with the corresponding unstratified Newcombe 95% CI, will be summarized by treatment group at Week 52. Subjects with missing data at Week 52 will be considered failures and counted as nonresponders.

In addition, if significant noncompliance with regulatory requirements during the course of the study is detected or reported at any clinical site, additional sensitivity analyses may be conducted on the primary efficacy endpoint by using the same approach but excluding all subjects from the noncompliant site(s).

6.1.2 Supplementary Analyses of Primary Efficacy Endpoint

No supplementary analyses of the primary efficacy endpoint are planned for this study.

6.2 Analyses of Key Secondary Efficacy Endpoints

Similarly to the primary endpoint, each secondary endpoint will be summarized by treatment group. Subjects with the intercurrent events defined in Section 2.2 and/or missing key secondary endpoint data at the Week 52 visit are considered failures. Each of the key secondary endpoints will be analyzed using the same approach as described for the primary efficacy endpoint using the following hypothesis:

$$H_0: \delta = 0$$

$$H_1: \delta \neq 0$$

Where δ is the common treatment difference across strata, $j=1$ to m . The common treatment difference is a weighted average of the stratum-specific treatment differences.

The estimate of the common treatment difference along with the corresponding stratified Newcombe 95% CI using the method of Yan and Su (2010) and CMH p-value will be presented for each active treatment group to corresponding placebo group (25 mg in induction placebo group or 75 mg in induction placebo group; placebo groups are not pooled) comparison.

The key secondary efficacy endpoints are:

- Endoscopic remission, as defined by centrally read endoscopic subscore 0 or 1 (modified, excludes friability), at the Week 52 visit.
- Clinical remission as defined by stool frequency subscore of 0 or 1 with at least a 1-point change from induction study (SHP647-301 or SHP647-302) baseline in SF subscore, and RB subscore of 0, at the Week 52 visit. Subjects with missing induction baseline value in SF subscore will be counted as clinical remission if both SF and RB subscores are 0 at Week 52.
- Sustained remission, ie, in remission at the SHP647-303 Week 52 visit, among subjects who were in remission at the time of MNT baseline (the observed value for the efficacy assessment at Week 12 in induction study). Remission is defined in Section 6.1.
- Clinical response based on composite score at the Week 52 visit. Clinical response (composite) is defined as a decrease from induction study (SHP647-301 or SHP647-302) baseline in the composite score of subject-reported symptoms using daily e-diary and centrally read endoscopy of at least 2 points and at least 30%, with an accompanying decrease in the subscore for rectal bleeding ≥ 1 point or a subscore for rectal bleeding ≤ 1 . Subjects with missing induction baseline value in the composite score but in remission by composite score will be counted as clinical response.
- Mucosal healing based on endoscopic and histologic assessment, at the Week 52 visit. Mucosal healing is defined by centrally read endoscopic subscore 0 or 1 (modified, excludes friability) and centrally read Geboes score of ≤ 2 .
- Glucocorticoid-free clinical remission at Week 52, among subjects using glucocorticoids at the MNT baseline. Glucocorticoid-free clinical remission is defined as clinical remission in addition to not requiring any treatment with glucocorticoids for at least 4 weeks prior to the Week 52 visit. Clinical remission is defined in second bullet above.
- Glucocorticoid-free remission at Week 52, among subjects using

glucocorticoids at the MNT baseline. Glucocorticoid-free remission is defined as remission in addition to not requiring any treatment with glucocorticoids for at least 4 weeks prior to the Week 52 visit. Remission is defined in Section 6.1.

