#### **Key Secondary Efficacy Endpoints:**

- Endoscopic remission, as defined by centrally read endoscopic subscore 0 or 1 (modified, excludes friability), at the Week 52 visit.
- Clinical remission as defined by SF subscore of 0 or 1 with at least a 1-point change from induction study (SHP647-301 or SHP647-302) baseline in SF subscore, and RB subscore of 0, at the Week 52 visit.
- Sustained remission, ie, in remission at the SHP647-303 Week 52 visit, among subjects who were in remission at the time of baseline in study SHP647-303. Remission is defined as a composite score of patient-reported symptoms using daily e-diary and centrally read endoscopy, with SF subscore of 0 or 1 with at least a 1-point change from induction study (SHP647-301 or SHP647-302) baseline, and RB subscore of 0, and endoscopic subscore of 0 or 1 (modified, excludes friability).
- Clinical response based on composite score at the Week 52 visit. Clinical response (composite) is defined as a decrease from induction study (SHP647-301 or SHP647-302) baseline in the composite score of subject-reported symptoms using daily e-diary and centrally read endoscopy of at least 2 points and at least 30%, with an accompanying decrease in the subscore for RB  $\geq 1$  point or a subscore for RB  $\leq 1$ .
- Mucosal healing, based on endoscopic and histologic assessment, at the Week 52 visit. Mucosal healing is defined by centrally read endoscopic subscore 0 or 1 (modified, excludes friability) and centrally read Geboes score of  $\leq 2$ .
- Glucocorticoid-free clinical remission at Week 52, among subjects using glucocorticoids at induction study baseline. Glucocorticoid-free clinical remission is defined as clinical remission in addition to not requiring any treatment with glucocorticoids for at least 4 weeks prior to the Week 52 visit. Clinical remission is defined as SF subscore of 0 or 1 with at least a 1-point change from induction study (SHP647-301 or

SHP647-302) baseline in SF subscore, and RB subscore of 0, at the Week 52 visit.

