- Glucocorticoid-free remission at Week 52, among subjects using glucocorticoids at induction study baseline. Glucocorticoid-free remission is defined as remission in addition to not requiring any treatment with glucocorticoids for at least 4 weeks prior to the Week 52 visit. Remission is defined as a composite score of subject-reported symptoms using daily e-diary and endoscopy, with SF subscore of 0 or 1 with at least a 1-point change from induction study (SHP647-301 or SHP647-302) baseline, and RB subscore of 0, and endoscopic subscore of 0 or 1 (modified, excludes friability).

Similar to the primary endpoints, the key secondary efficacy endpoints will all be tested by the following hypothesis:

$$H_0: \delta = 0$$

$$H_1: \delta \neq 0$$

The key secondary endpoints will be analyzed using the same approach as described for the primary endpoint. Subjects with missing key secondary endpoint data at the Week 52 visit will be considered failures and counted as nonresponders.

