			Appendix 16.5 or discontinuation.		
Key Secondary	6th key secondary estimand is the effect of ontamalimab compared to placebo at Week 52 in impact on glucocorticoid-free clinical remission.	16- to 80-year-old adolescents and adults with UC defined through inclusion and exclusion criteria as stated in the protocol	Glucocorticoid-free clinical remission at the Week 52 visit, among subjects using glucocorticoids at induction study baseline, defined as clinical remission in addition to not requiring any treatment with glucocorticoids for at least 4 weeks prior to the Week 52 visit. Clinical remission is defined as stool frequency subscore of 0 or 1 with at least a 1-point change from induction study	Composite: intercurrent events captured in variable definition	Difference in proportions of subjects with glucocorticoid-free clinical remission at the Week 52 visit between each active treatment group (25 mg or 75 mg ontamalimab) and the corresponding placebo (25 mg in induction placebo group or 75 mg in induction placebo group; placebo groups are not pooled)

Estimand	Definition	Attributes			
		A: Population	B: Variable	C: Strategy for Addressing Intercurrent Event	D: Population-level Summary
			(SHP647-301 or SHP647-302) baseline in stool frequency subscore, and rectal bleeding subscore of 0, at the Week 52 visit, without treatment failure or rescue therapy defined in Appendix 16.5 or discontinuation.		

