
Key Secondary
	
7th key secondary estimand is the effect of ontamalimab compared to placebo at Week 52 in impact on glucocorticoid-free remission.
	
16- to 80-year-old adolescents and adults with UC defined through inclusion and exclusion criteria as stated in the protocol
	
Glucocorticoid-free remission at the Week 52 visit, among subjects using glucocorticoids at induction study baseline, defined as remission in addition to not requiring any treatment with glucocorticoids for at least 4 weeks prior to the Week 52 visit. Remission is defined as a composite score of subject-reported symptoms using daily e-diary and endoscopy, with stool frequency subscore of 0 or 1 with at least a 1-point change from induction study (SHP647-301 or SHP647-302) baseline, and rectal bleeding subscore of 0, and endoscopic
	
Composite: intercurrent events captured in variable definition
	
Difference in proportions of subjects with glucocorticoid-free remission at the Week 52 visit between each active treatment group (25 mg or 75 mg ontamalimab) and the corresponding placebo (25 mg in induction placebo group or 75 mg in induction placebo group; placebo groups are not pooled)

----------------------	---	---	---	---	---

Estimand	Definition	Attributes			
		A: Population	B: Variable	C: Strategy for Addressing Intercurrent Event	D: Population-level Summary
			subscore of 0 or 1 (modified, excludes friability), without treatment failure or rescue therapy defined in Appendix 16.5 or discontinuation.		

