2.3.2 Key Secondary Endpoints

- Endoscopic remission, as defined by centrally read endoscopic subscore 0 or 1 (modified, excludes friability), at the Week 52 visit.
- Clinical remission, as defined by SF subscore of 0 or 1 with at least a 1-point change from induction study (SHP647-301 or SHP647-302) baseline in SF subscore, and RB subscore of 0, at the Week 52 visit.
- Sustained remission, ie, in remission at the SHP647-303 Week 52 visit, among subjects who were in remission at the time of baseline in Study SHP647-303. Remission is defined as a composite score of patient-reported symptoms using daily e-diary and centrally read endoscopy, with SF subscore of 0 or 1 with at least a 1-point change from induction study (SHP647-301 or SHP647-302) baseline, and RB subscore of 0, and endoscopic subscore of 0 or 1 (modified, excludes friability).
- Clinical response based on composite score at the Week 52 visit. Clinical response (composite) is defined as a decrease from induction study (SHP647-301 or SHP647-302) baseline in the composite score of subject-reported symptoms using daily e-diary and centrally read endoscopy of

at least 2 points and at least 30%, with an accompanying decrease in the subscore for RB ≥ 1 point or a subscore for RB ≤ 1 .

- Mucosal healing based on endoscopic and histological assessment at the Week 52 visit. Mucosal healing is defined by centrally read endoscopic subscore 0 or 1 (modified, excludes friability) and centrally read Geboes score of ≤ 2 .
- Glucocorticoid-free clinical remission at Week 52, among subjects using glucocorticoids at induction study (SHP647-301 or SHP647-302) baseline. Glucocorticoid-free clinical remission is defined as clinical remission in addition to not requiring any treatment with glucocorticoids for at least 4 weeks prior to the Week 52 visit. Clinical remission is defined as SF subscore of 0 or 1 with at least a 1-point change from induction study (SHP647-301 or SHP647-302) baseline in SF subscore, and RB subscore of 0, at the Week 52 visit.

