- Glucocorticoid-free remission at Week 52, among subjects using glucocorticoids at induction study (SHP647-301 or SHP647-302) baseline. Glucocorticoid-free remission is defined as remission in addition to not requiring any treatment with glucocorticoids for at least 4 weeks prior to the Week 52 visit. Remission is defined as a composite score of subject-reported symptoms using daily e-diary and endoscopy, with SF subscore of 0 or 1 with at least a 1-point change from induction study (SHP647-301 or SHP647-302) baseline, and RB subscore of 0, and endoscopic subscore of 0 or 1 (modified, excludes friability).

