5.2 Demographic and Other Baseline Characteristics

Descriptive summaries of demographic and baseline characteristics will be presented by treatment group as listed in Appendix 16.6 for the Safety Set, Ontamalimab Responder FAS, and Placebo Responder FAS.

Subject's age is from the induction study (SHP647-301 or SHP647-302), which is calculated as the difference between the date of birth and the date of informed consent in the induction study. If day of birth is missing then the day will be imputed as 1, if both the day and month of birth are missing then the day will be imputed as 1 and the month will be imputed as 1 (January). The following demographic characteristics will be summarized in the following order in the tables: age, age category (<18, 18 to <65 and ≥ 65 ; <35 and ≥ 35), sex (Male, Female), ethnicity (Hispanic or Latino, Not Hispanic or Latino, Not Reported, Unknown), region (North America, Western Europe, Eastern Europe, Asia (Japan/South Korea), ROW (Africa/Australia/Latin America/Middle East), race (American Indian or Alaska Native, Asian (Japanese, Korean, Other), Black or African American, White, Native Hawaiian or Other Pacific Islander, and Other), Japanese ancestry (Currently living in Japan, Born in Japan and currently living outside of Japan for less than 5 years, and Other), and Korean ancestry (Currently living in Korea, Born in Korea and currently living outside of Korea for less than 5 years, and Other).

Baseline is defined as the last assessment prior to the first administration of the IP in the induction study (SHP647-301 or SHP647-302) unless otherwise specified. Maintenance (MNT; SHP647-303) baseline is defined as the value for the assessment collected at the Week 12 visit of the induction study. The following baseline characteristics will be summarized:

- Weight,
- Height,
- Body mass index (BMI),
- UC disease duration and UC disease duration category (<1 year, ≥ 1 to <3 years, ≥ 3 to <7 years and ≥ 7 years)

Disease duration is calculated as the number of years from the date of UC diagnosis to the date of informed consent in the induction study (SHP647-301 or SHP647-302),

- UC disease location (Proctitis, Procto-Sigmoiditis, Left-sided Colitis, Extensive Colitis/Pancolitis),
- Total Mayo severity and total Mayo severity category (<6, 6 to <9, and ≥9),
- Total Mayo severity and total Mayo severity category at MNT baseline (<6, 6 to <9 and ≥9),
- Stool frequency score (0, 1, 2, and 3),

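### SAP 6.2 tests both glucocorticoid-free key secondary endpoints in users at maintenance baseline; the protocol and the SAP's own estimands define them in users at induction baseline

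*SAP*

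**What the plan says.** Two endpoints are each defined in four sections, which gives eight statements. All eight use induction baseline:

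- Protocol synopsis and Protocol 9.8.2.1: "Glucocorticoid-free clinical remission at Week 52, among subjects using glucocorticoids at induction study baseline" and "Glucocorticoid-free remission at Week 52, among subjects using glucocorticoids at induction study baseline".
- SAP 2.2, Table 1, 6th and 7th key secondary estimands: "among subjects using glucocorticoids at induction study baseline, defined as clinical remission in addition to not requiring any treatment with glucocorticoids" and "among subjects using glucocorticoids at induction study baseline, defined as remission in addition to not requiring any treatment with glucocorticoids".
- SAP 2.3.2: "Glucocorticoid-free clinical remission at Week 52, among subjects using glucocorticoids at induction study (SHP647-301 or SHP647-302) baseline" and "Glucocorticoid-free remission at Week 52, among subjects using glucocorticoids at induction study (SHP647-301 or SHP647-302) baseline".

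SAP 6.2, which specifies the analysis, has "Glucocorticoid-free clinical remission at Week 52, among subjects using glucocorticoids at the MNT baseline", and its bullet for glucocorticoid-free remission uses the same MNT-baseline restriction.

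The two time points differ. SAP 5.2 states: "Maintenance (MNT; SHP647-303) baseline is defined as the value for the assessment collected at the Week 12 visit of the induction study". Induction baseline is the last assessment before the first induction dose. SAP 14, which lists departures from Protocol Amendment 3, has one entry, on the total sign/symptom score.

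**The concern.** A confirmatory test needs one analysis population. Here the text supports two for each endpoint, and so two possible p-values per dose comparison. A subject who used glucocorticoids at induction baseline but had stopped by Week 12 counts under the protocol and not under SAP 6.2. A subject who started during induction counts only under SAP 6.2.

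Both endpoints belong to the family for which SAP 6.4 claims strong control of the family-wise error rate, and formal testing goes ahead despite early closure (Protocol 9.6, SAP 3.4). The sensitivity analysis and the placebo-responder summaries in SAP 6.2.1 inherit the ambiguity.

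Timing adds weight. SAP 3.3 treats this study as unblinded once SHP647-304 is unblinded, which is planned before this study's database lock. A denominator chosen after that point would be chosen with treatment assignments accessible.

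**Working it through.** **Are the two populations the same by definition?** No. SAP Appendix 16.4 gives two rules. Glucocorticoid use at baseline looks at the 6 days before the first induction dose. Glucocorticoid use at MNT baseline looks at the 6 days before the dose at induction Week 12. SAP 5.2 tabulates the two flags on separate rows.

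**Scope.** The alpha-controlled family has (1 primary + 7 key secondary) × 2 doses = 16 tests. Affected: 2 endpoints × 2 doses = 4.

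**Consequence for the CMH test.** SAP 6.1 stratifies by three binary factors: glucocorticoid use at MNT baseline, prior anti-TNF treatment, and remission in induction. SAP 6.2 applies the same approach.

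- Users at induction baseline: up to 2 × 2 × 2 = 8 strata.
- Users at MNT baseline: the glucocorticoid factor is constant, so at most 1 × 2 × 2 = 4 strata.

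**Which population did the power calculation use?** Footnote b of Protocol Table 8 and SAP Table 2 assumes that 58% are on corticosteroids at the baseline of this study. Inputs: 148 per arm, 0.58 × 148 = 85.8, taken as n = 85, and the rates in the tables. The formula is the pooled-variance two-proportion test:

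Power = Φ{ [ |p₁ − p₂| − z·√(2p̄(1 − p̄)/n) ] / √( (p₁(1 − p₁) + p₂(1 − p₂))/n ) }

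The column alphas of .05 and .001 are each halved across the two doses, so z = 2.241 at .025 and 3.481 at .0005 (two-sided).

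For 50% vs 19%: p̄ = 0.345, null SE = 0.0729, alternative SE = 0.0689.

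- .025: (0.31 − 2.241 × 0.0729)/0.0689 = 2.13, power 0.983.
- .0005: (0.31 − 3.481 × 0.0729)/0.0689 = 0.82, power 0.793.

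| Endpoint | Rates | Computed (.025 / .0005) | Stated |
|---|---|---|---|
| Glucocorticoid-free clinical remission | 50% vs 19% | 0.983 / 0.793 | 0.98 / 0.79 |
| Glucocorticoid-free remission | 45% vs 14% | 0.990 / 0.844 | 0.99 / 0.84 |

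The stated figures reproduce, so 58% of 148 was used. The arithmetic cannot show which baseline the 58% describes; that rests on the footnote's wording. Footnote a supports reading it as MNT baseline: it uses the same phrase for subjects in remission, and the sustained-remission endpoint is defined by remission at SHP647-303 baseline. On that reading the power text agrees with SAP 6.2 and not with the eight definitions.

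**What if induction baseline is used?** The documents give no induction-baseline share. If it is assumed to be 40% to 75% (59 to 111 per arm as planned), power at .025 runs from 0.916 to 0.997 for glucocorticoid-free clinical remission and from 0.939 to 0.999 for glucocorticoid-free remission. At the 366 enrolled, assuming the planned 592/696 mix, there are 366 × 592/696 ÷ 4 = 77.8 per arm. The same shares then give 31 to 58 users per arm, and power of 0.635 to 0.911 and 0.678 to 0.934.

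**The case against.** The conflict cannot be explained away by a redaction or a missing figure. The case for treating it as minor is as follows.

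- **It may be a slip.** SAP 2.2 and 2.3.2 still say induction baseline, so SAP 14 may have had no intended change to declare. This stands: the documents do not show which was meant. A slip in the section that specifies the analysis still needs correcting.
- **The eight statements are partly repeats, and other text leans to MNT baseline.** Randomisation is stratified on glucocorticoid use at SHP647-303 baseline, both power footnotes refer to the baseline of this study, and tapering starts on maintenance Day 1. This is fair, and it is why a route is offered for each population.
- **A constant factor drops out of a CMH test by itself.** This is true, and the test stays valid. Sustained remission has the same feature. The strata count is a consequence of the choice, not a second error.
- **The power rows are superseded planning figures.** This is also fair. They show where the inconsistency extends but do not size it, and a clarifying note would be enough.
- **Formal testing may never reach these endpoints.** If alpha passes in the listed order (the figure is not shown), both come after five other key secondary endpoints. Mucosal healing alone, at 30% vs 13% with about 78 per arm, has power of about 0.64 at .025, before early-closure subjects with missing Week 52 data count as failures. This lowers the likely impact but does not settle which population is tested.

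**Conclusion.** The contradiction is explicit and holds. SAP 6.2 as written tests a different population from the protocol and from the SAP's own 6th and 7th key secondary estimands, in 4 of 16 alpha-controlled tests. The primary and the first five key secondary endpoints are unaffected.

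The effect on estimates or p-values cannot be derived from the documents and may be small if the populations overlap almost completely. That uncertainty is a reason to settle the population before unblinding. Two points rest on reading rather than arithmetic: that the 58% refers to MNT baseline, and that alpha passes in the listed order. The conclusion depends on neither. It must be fixed because following one part of the SAP contradicts another.

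**What to change.** Use one population throughout and fix it before unblinding.

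**Default.** Change the two SAP 6.2 bullets to users at induction study baseline, matching the protocol, SAP 2.2 and SAP 2.3.2. In Protocol Table 8 and SAP Table 2, either state that the two power rows refer to the MNT-baseline subset, or re-base them on an induction-baseline share. The 58% cannot simply be relabelled, since no induction-baseline share is given. Cost: two bullets and two footnote clarifications, one in each document.

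**If MNT baseline is intended.** Change the two rows of SAP Table 1 and the two bullets in SAP 2.3.2, record the departure from the protocol in SAP 14, and add a sentence that the glucocorticoid stratum drops out of the CMH test for these two endpoints. Cost: those six text edits.

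Neither route needs new data or a new derivation, because both flags are already defined in Appendix 16.4.
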